**I. Withdrawal**

Occurrence of death, rescinded consent, randomization failure after surgery commenced, or when the subject has a complete removal, or revision of metal components (femoral component / tibial tray).

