**G. Safety**

1. Adverse Events: Please reference section **6**, and section **15** for Adverse event data collection method and definitions. Only serious and device related adverse events will be collected for this study. Patient hospital readmissions should be documented on an adverse event form, and the relation to the device documented.
2. Revisions / Removals: Please reference section **4** and section **15** for Revision / Removal data collection method and definitions.
3. Withdrawals: Please reference section **3.4** for detailed data collection methods, and section **15** for relative definitions.
4. Protocol Deviations: Please reference section **5** for Protocol Deviation data collection methods for this study.

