**3. SELECTION AND WITHDRAWAL OF SUBJECTS**

- A. Process: Patients will be screened according to the inclusion / exclusion criteria detailed in Section 3.1 and 3.2. If a patient consents to participate but is found to be ineligible prior to commencement of first bony cut intraoperatively, this will be documented on the screening log.
- B. Screen Failures: A screen failure can occur up to and prior to the first bony cut of the surgical technique. The ACL should be assessed intraoperatively to screen out any patients without sufficient soft tissue to participate, and if insufficient documented on the screening log as a screen failure. In the event that the patient receives a non randomized study device AFTER the first bony cut has commenced due to surgeon discretion, this patient is considered a randomization failure, but will still be followed in the study. Any patient consented that is a screen failure will not count towards the sample size, and will be replaced.

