**3.3. SUBJECT ENROLLMENT****A. Definition of Study Enrollment :**

1. A patient is considered enrolled after they have been preoperatively screened for eligibility, consented to participate, and after surgeon's first intraoperative bony cut:
  - a. Received a randomized study component.
  - b. Received a non-randomized study component (randomization failure) due to surgeon discretion and standard of care at the local center.
2. Enrolled patients will be documented on the Enrollment form.

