**B. Randomization Failures:**

1. A randomization failure is a patient who has been randomized but does not receive the intended randomized treatment. These patients' randomization assignments will not be re-used, and randomization should continue with the next patient being screened and consented.
  - a. If the randomization failure occurs prior to the first bony cut, the patient is not considered "enrolled" and this should be documented on the screening log as a "screen failure" with the reason and rationale described (e.g. insufficient ACL). No further data should be collected on this patient. Screen failures do not count towards the sample size and will be replaced.
  - b. If the randomization failure occurs after the surgery has commenced with the first bony cut, but due to the surgeon's discretion, the randomized treatment will not be the best treatment for the patient, the surgeon should implant according to their discretion and standard of care at the center. This patient counts toward the overall sample size and will not be replaced. Data should be collected on these patients per protocol.

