**3.4. SUBJECT WITHDRAWAL****A. Voluntary Participation:**

It is recognized that the subject's participation in this trial is entirely voluntary, and that she/he may refuse to participate and may withdraw from participation at any time without jeopardy to any future medical care. It is also recognized that the investigator, at his/her discretion, may withdraw a subject from this study based upon his/her professional judgment. In event of subject withdrawal, applicable local procedures should be followed. Patients who are withdrawn from the study will not be replaced, and a Withdrawal form should be completed.

**B. Withdrawals:** All subject withdrawals must be documented on the Withdrawal Form. If withdrawal is due to patient death, or removal of components as indicated below, a withdrawal form should be completed. If the patient is withdrawn after receiving the randomized treatment, the subject will NOT be replaced.

**C.** If a patient receives a partial revision (patella or polyethylene replacement), or a reoperation (e.g.: manipulation), this should be documented on an adverse event form and the patient should continue to be followed in the study.

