**D. Subject Withdrawal Criteria:**

1. If patients meet any of the following criteria, a subject withdrawal form should be completed, and below data documented on the form:
  - a. Patient rescinds consent in writing: Date of occurrence
  - b. Patient Death: Reason and date of death should be documented, and any relation to study device.
  - c. Removal: Date of revision, all component part numbers removed, reason for revision, and any relation to study device.
  - d. Revision of Metal\* Components (Femur or Tibia): date of revision, all component part numbers removed, and reason for revision

*\*Bearing revisions in which only the polyethylene is replaced will not be withdrawn from the study.*

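### Section 15 I makes a post-cut randomization failure a withdrawal, Sections 3 B and 3.3 B keep the same patient in follow-up, and Section 8 names no analysis set to settle where that knee is analysed

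*Combined protocol and SAP*

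**What the plan says.** Section 15 I counts as a withdrawal: "Occurrence of death, rescinded consent, randomization failure after surgery commenced, or when the subject has a complete removal". Section 2.7 G gives that definition standing, because for withdrawals it sends the reader to Section 3.4 "for detailed data collection methods, and section 15 for relative definitions".

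The operative sections treat the same event differently:

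- Section 3 B, on a patient given a non-randomized device after the first bony cut: "this patient is considered a randomization failure, but will still be followed in the study".
- Section 3.3 A counts as enrolled a patient who "Received a non-randomized study component (randomization failure) due to surgeon discretion and standard of care at the local center".
- Section 3.3 B.1.b: "This patient counts toward the overall sample size and will not be replaced. Data should be collected on these patients per protocol".
- Section 3.4 D opens its list with "If patients meet any of the following criteria, a subject withdrawal form should be completed, and below data documented on the form". It then names rescinded consent, death, removal and revision of metal components. Randomization failure is not listed.

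On analysis, Section 8.2 specifies a two-sided Pearson chi-square test at 0.05, and Section 8.3 lists tests for the other measures. No part of Section 8 names an analysis set or says in which arm a switched knee is analysed. Section 9 deals with data entry, reimbursement and telephone follow-up. Sections 1.1, 2.2 and 8.1 A describe the groups by the device received. Section 2.4 has the database assign the treatment group.

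**The concern.** One event carries two instructions. Under Section 15 I the patient is a withdrawal. Under Sections 3 B and 3.3 B the patient is followed and contributes data. With no analysis set in Section 8, three treatments of these knees are compatible with the text: leave them out as withdrawn, analyse them as randomized, or analyse them by implant received.

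The switch happens after randomization and at the surgeon's discretion, so it may be related to prognosis. Section 1.2 gives a reason why switching could be unequal between arms: XP needs a functional ACL, whereas CR requires the ACL to be sacrificed. If switched knees differ from the rest, the first and third treatments no longer compare groups formed by randomization. The primary endpoint is the comparison affected, and the choice could be made after the outcomes are known.

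**Working it through.** **Same patients?** Section 15 I speaks of a failure after surgery has commenced. Section 3.3 B.1.b places that moment at the first bony cut. Both therefore refer to the same patients.

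**What conflicts.** Enrolment, counting and non-replacement do not: Section 3.4 A also leaves withdrawn patients unreplaced, and patients who die or are revised were enrolled and counted too. The conflict is withdrawal against continued follow-up with data collection. No section says outright that withdrawal ends data collection. Section 3.4 C implies it, since for partial revisions and reoperations, which are not withdrawals, it says "this should be documented on an adverse event form and the patient should continue to be followed in the study".

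**Plan's own figure (Section 8.1).** Proportions 0.66 and 0.83, two-sided alpha 0.05, power 90%, pooled proportion 0.745:

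n = [1.960·√(2·0.745·0.255) + 1.282·√(0.66·0.34 + 0.83·0.17)]² / 0.17² = (1.208 + 0.775)² / 0.0289 = 136.05, so 137 per arm (power 0.902). Then 137/0.90 = 152.2, so 153 per arm and 306 in total. The plan's figures reproduce.

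**Illustration with no device effect.** The documents give none of the following, so they are assumptions:

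- Group 1 (0.66) is CR; the table does not label the groups.
- 137 evaluable knees per arm, with 66% normal in each arm as randomized.
- A share c of XP-assigned knees is switched to CR, and none the other way.
- A proportion q of the switched knees feels normal.

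Formulas:

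- Unswitched XP rate: g = (0.66 − c·q)/(1 − c).
- Dropped: g on 137(1 − c) knees against 0.66 on 137.
- By implant received: g on 137(1 − c) knees against (0.66 + c·q)/(1 + c) on 137(1 + c).
- Rejection = 1 − Φ((1.96·s0 − d)/s1) + Φ((−1.96·s0 − d)/s1), where d is the expected difference, s0 the pooled and s1 the unpooled standard error.

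Worked case, c = 5% (about 7 knees), q = 0.30, dropped: g = 0.645/0.95 = 0.6789, d = 0.0189, s0 = 0.0576, s1 = 0.0576. Rejection = 0.051 + 0.011 = 6.2%.

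| c | q | Dropped: difference, rejection | By implant: difference, rejection |
|---|---|---|---|
| 3% | 0.50 | 0.5 points, 5.1% | 1.0 points, 5.3% |
| 3% | 0.30 | 1.1 points, 5.4% | 2.2 points, 6.6% |
| 5% | 0.50 | 0.8 points, 5.2% | 1.6 points, 5.9% |
| 5% | 0.30 | 1.9 points, 6.2% | 3.6 points, 9.6% |
| 10% | 0.50 | 1.8 points, 6.0% | 3.2 points, 8.6% |
| 10% | 0.30 | 4.0 points, 10.5% | 7.3 points, 24% |

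Positive differences favour XP. At q = 0.66 the bias is zero. At q = 0.75 and c = 5% it is −0.5 points (dropped) and −0.9 points (by implant). If all switching ran from CR to XP, every sign would reverse. Analysis as randomized holds 5% throughout.

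**Illustration with a true 17-point gain in unswitched XP knees and none in switched ones.** As randomized, the difference is 0.17(1 − c):

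| c | Difference as randomized | Power, 137 per arm |
|---|---|---|
| 0% | 17.00 points | 0.90 |
| 3% | 16.49 points | 0.88 |
| 5% | 16.15 points | 0.87 |
| 10% | 15.30 points | 0.82 |

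At c = 5% and q from 0.50 to 0.30, the same knees give 16.15 points as randomized, 17.8-18.9 if dropped and 18.6-20.6 by implant received.

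**The case against.** The strongest reply is that Section 15 I is one clause in a list of definitions, outnumbered by explicit instructions. Sections 3 B and 3.3 B require follow-up, Section 3.4 D omits the event, and nothing tells a site to stop collecting data. That stands, and it limits the practical conflict. A reader might infer that sites are told to abandon these patients; the documents do not say so. It does not dispose of the point, because Section 2.7 G sends readers to Section 15 for the definitions and an analyst could exclude withdrawn patients on that authority.

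A second reply is that receiving a device is ordinary language for describing an arm, and that Section 2.4 and the retention of switched patients in Section 3.3 lean towards analysis as randomized. That is fair. A reader might infer that the plan has chosen analysis by implant received; it has not. Neither wording is an analysis rule, so the choice is still open.

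A third reply is that the arithmetic is all assumption, and that ACL screening before the first cut should remove one obvious cause of switching. That also stands. With 3-5% switching and knees dropped, rejection is only 5.1-6.2%. The 24% figure needs 10% one-way switching, 30% normal in switched knees and analysis by implant received, all together.

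**Conclusion.** The point holds in this form: the documents contradict themselves on whether a post-cut randomization failure is a withdrawal or stays in follow-up, and Section 8 does not say how such knees enter the primary comparison. It needs correcting before analysis, because the primary analysis population of a randomized trial is undefined for patients selected by a decision made after randomization.

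Three stronger readings are not supported. The enrolment, counting and replacement rules do not conflict with withdrawal. The sample size is not miscalculated. Nor do the documents show that the result will favour XP or that the type I error will be materially inflated: with no switch rate, direction or prognosis given, the bias could be nil, small, larger or reversed. The conclusion rests on the contradiction and the missing analysis set, not on the illustrative figures.

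**What to change.** 1. Reconcile Section 15 I with Sections 3 B, 3.3 B and 3.4 D by deleting randomization failure after surgery commenced from the withdrawal definition. The surgeon's choice of implant is untouched.

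2. Add to Section 8.2, for example: The primary analysis compares enrolled knees (those past the first bony cut) in the arm to which they were randomized, using all knees with an observed primary outcome. Sensitivity analyses will address missing outcomes and will compare knees by implant received, listing separately any knee given an implant from neither arm.

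The missing-outcome analysis is needed because Section 8.1 B expects 10% loss and Section 9 gives no analysis rule for it. The separate listing is needed because Section 3.3 B.1.b lets the surgeon implant at discretion, which may leave room for a device from neither arm.

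Cost: no new data, since Section 3.3 B.1.b already requires them. The statistical price is the dilution shown above: power of 0.88, 0.87 or 0.82 at an assumed 3, 5 or 10% switching. Restoring 90% would take 170 or 193 per arm at 5% or 10%, against 153 planned. No added enrolment is proposed, because the switching rate is unknown. Failures before the first cut, of which Section 3.3 B.1.a says "Screen failures do not count towards the sample size and will be replaced", are a separate matter that this change does not address.

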**2.3. NUMBER OF SITES AND SUBJECTS/PROCEDURES**

A total of 306 cases (knees) will be included in this study from four centers; 153 Vanguard CR and 153 Vanguard XP. Sample size calculation is provided in Section 8.1.

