**2.4. RANDOMIZATION**

Patients will be randomized using a 1:1 blocked randomization scheme. Bilateral patients should be randomized by knee. Randomization will occur by enrolling the patient into Joint Assist and assigning an operative date. At that point the electronic database will assign the treatment group for the patient. The patient will be blinded from treatment until surgery has occurred.

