**3.1. INCLUSION CRITERIA**

Subjects will be considered for inclusion in this trial if they satisfy the following study criteria\* and FDA cleared indications for use:

- A. Cemented application of components\*
- B. Bilateral subjects randomized by knee\*
- C. Patients with pre-existing contralateral knee surgery\*
- D. Painful and disabled knee joint resulting from osteoarthritis, rheumatoid arthritis or traumatic arthritis where one or more compartments are involved.
- E. Correction of varus, valgus, or posttraumatic deformity
- F. Sufficient soft tissue surrounding the knee, including the Anterior Cruciate Ligament.

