### **4. REVISION / REMOVAL**

For subjects whom are revised in which a partial (revision) or full revision (removal) is conducted, an adverse event form should be completed. In patients in which metal or all components (removal) are removed, a withdrawal form should also be completed.

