**8. STATISTICAL ANALYSIS****8.1. SAMPLE SIZE JUSTIFICATION**

A. The primary goal of this study is to determine whether subjects receiving a Vanguard XP knee would feel more “normal/asymptomatic” than subjects who are implanted with a Vanguard CR knee. This will be achieved using Pearson Chi-Square test for two independent proportions.

Fixed Scenario Elements	
Distribution	Asymptotic normal
Method	Normal approximation
Number of Sides	2
Null Proportion Difference	0
Group 1 Proportion	0.66
Group 2 Proportion	0.83
Alpha	0.05

B. Based on these assumptions, 137 patients will give 90% power to detect a 17 percent difference between groups with regard to the percentage of patients who report their knee as feeling “normal”. We increase our sample size by 10% to allow for patients who do not follow up for various reasons. This gives a sample size of 153 for each group and a total of 306 patients.

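### Withdrawal after removal or metal revision is written for the subject, not the randomized knee; read literally, it also withdraws a bilateral patient's intact study knee

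*Combined protocol and SAP*

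**What the plan says.** **Unit of randomization and counting.** Section 2.4 states "Bilateral patients should be randomized by knee", and section 3.1 B lists "Bilateral subjects randomized by knee" among the inclusion criteria. Section 2.3 counts knees: "A total of 306 cases (knees) will be included in this study from four centers; 153 Vanguard CR and 153 Vanguard XP". Section 8.1 gives the same total in persons: "This gives a sample size of 153 for each group and a total of 306 patients".

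**Unit of withdrawal.** Section 15 I includes in its definition of withdrawal the case "or when the subject has a complete removal, or revision of metal components (femoral component / tibial tray"). Section 3.4 D opens "If patients meet any of the following criteria, a subject withdrawal form should be completed, and below data documented on the form", and its list puts removal and metal revision beside death and rescinded consent. Section 4 adds "In patients in which metal or all components (removal) are removed, a withdrawal form should also be completed". None of the three names the affected knee or mentions a second study knee. Under section 3.4 B, a subject withdrawn after receiving the randomized treatment is not replaced.

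**What stays in follow-up.** Section 3.4 C keeps patients with a partial revision (patella or polyethylene) or a reoperation in the study. The footnote to 3.4 D repeats this for polyethylene-only revisions.

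**Endpoint concerned.** Survivorship is a secondary endpoint (section 2.5 B) and, through 10 years, a stated purpose (section 1.4 C).

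**The concern.** Death and rescinded consent happen to a person. Removal and metal revision happen to a knee. The protocol puts all four under one subject-level rule in a trial where one person may contribute two randomized knees, possibly one in each arm.

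Take a bilateral patient with CR in one knee and XP in the other. If the CR femoral component is revised in year 3, a site following 3.4 D and 15 I to the letter withdraws the subject, and the XP knee leaves with it. Another site might keep the XP knee. Nothing in the text decides between them.

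The stake is mainly survivorship. An intact knee would be censored because of a failure in the same person. If the failure risks of a patient's two knees are positively correlated, the knees removed are those at higher risk, and later failure is understated. In patients with one knee in each arm, each failure in one arm removes an at-risk knee from the other. The arm with fewer failures then loses more intact knees, and the effect need not cancel. Section 8.3 offers no safeguard: it lists t, Wilcoxon, ANOVA, Fisher and likelihood ratio chi-square tests, with no censoring rule and no handling of paired knees.

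**Working it through.** **1. The plan's own figure.** Inputs from section 8.1: proportions 0.66 and 0.83, two-sided alpha 0.05, power 90%. With the pooled-variance normal approximation and mean proportion 0.745:

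n = [1.960 × √(2 × 0.745 × 0.255) + 1.282 × √(0.66 × 0.34 + 0.83 × 0.17)]² / 0.17² = 136.05, rounded up to 137 per group.

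Inflating for 10% loss: 137 / 0.9 = 152.2, rounded up to 153 per group, 306 in total. Both figures reproduce. Power at 137 per group is 90.2%.

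**2. Intact knees affected under the literal reading.** The documents give neither input, so both are assumptions: b, the share of the 306 knees belonging to patients with both knees in the study, and f, the risk that a knee has a removal or metal revision. With the two knees independent, the expected number of intact knees whose partner fails is 306 × b × f × (1 − f).

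| b | f | Intact knees affected | Failures per arm (153 × f) |
|---|---|---|---|
| 10% | 3% | 306 × 0.10 × 0.03 × 0.97 = 0.9 | 4.6 |
| 20% | 5% | 306 × 0.20 × 0.05 × 0.95 = 2.9 | 7.7 |
| 30% | 8% | 306 × 0.30 × 0.08 × 0.92 = 6.8 | 12.2 |

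This is about 1 to 7 knees, or 0.3% to 2.2% of 306. A wider grid runs from 0.3 knees (b = 5%, f = 2%) to 11.0 (b = 40%, f = 10%; 3.6% of 306).

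**3. Effect on the primary test.** As a worst case, let every such loss come on top of the planned 10% and before the primary assessment, split evenly between arms. Power is then 89.9% after 3 lost knees, 89.6% after 6 and 89.0% after 11, against 90.2%.

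**4. Effect on survivorship.** The failures that would go unseen among the censored knees are at most (knees affected) × f under independence: 0.9 × 3% = 0.03, 2.9 × 5% = 0.15 and 6.8 × 8% = 0.54. Tripling the last figure as an allowance for within-person correlation gives about 1.6, against 306 × 8% = 24.5 failures in all.

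**5. Does withdrawal mean that follow-up ends?** Sections 3.4 C and 3.4 D (footnote) keep partial and polyethylene-only revisions in follow-up, which implies by contrast that metal revision or removal ends it. Against this, 15 I also lists randomization failure after the start of surgery as a withdrawal, while sections 3 B and 3.3 B keep those patients under follow-up. The term is therefore not used consistently. The text neither stops nor continues follow-up of a second study knee.

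**The case against.** The best reply is that subject and patient are used loosely for the case. Section 2.3 counts 306 knees and section 8.1 calls the same number patients. In the 3.4 D footnote, what is not withdrawn is a bearing revision, not a person. On that view 15 I already means the failed knee. The reading is possible, but no section states it, and the rule sits beside two events that can only apply to a person. The reply shows ambiguity; it does not show that the intact knee is protected.

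Four stronger inferences should be resisted.

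- *That the protocol ends follow-up of the other knee.* No section says so. Sections 3.4 D and 4 require a form. Where the protocol wants data collection to stop, as for screen failures in 3.3 B, it says so. The inconsistency over randomization failures also means that 15 I alone cannot establish the point.
- *That the losses are large.* Censored knees should be set against knees at risk, not against failures per arm, and they are then about 2% or less in the main range. If failures are spread over ten years, most intact knees would already have their 1- and 2-year clinical and radiographic data, since Table 2.6-A schedules only PROMS as a routine form after that.
- *That same-patient comparisons of the devices are lost.* None is planned; sections 8.2 and 8.3 specify unpaired tests.
- *That the withdrawal form has no field for side.* The form is not in the documents, so this cannot be checked.

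One part of the objection stands and affects the remedy. Continued follow-up has a small cost: a person-level score such as EQ-5D, collected for the intact knee after the partner's revision, may reflect the other knee.

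**Conclusion.** The concern holds as a mismatch of units with a poor literal consequence. Randomization and the case count are by knee, withdrawal after removal or metal revision is by subject, and there is no exception for a second study knee. A site that follows the text literally would withdraw an intact randomized knee because its partner failed.

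The size is modest: about 1 to 7 of 306 knees, on an assumed 10-30% of knees in bilateral study patients and an assumed 3-8% failing, with the two knees independent. The effect on primary power is negligible. What remains is avoidable censoring in the 10-year survivorship endpoint. It would be informative only to the extent that a patient's two knees share risk, and the documents give no figure for that. The change is worth making because it is cheap and because follow-up not collected over ten years may not be recoverable later.

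**What to change.** In sections 3.4 D, 4 and 15 I, state that removal or metal revision ends study follow-up for the affected study knee only, and that a contralateral study knee continues on the schedule of Table 2.6-A. Bring section 3.4 B into line. Keep death and rescinded consent at subject level. Make sure that the withdrawal record identifies which knee is withdrawn. While 15 I is open, reconcile its entry on randomization failures with sections 3 B and 3.3 B.

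In section 8.3, state how the second knee of a bilateral patient is censored and how within-patient correlation is handled in the survivorship analysis. Flag person-level scores collected for an intact knee after its partner's revision, so that they can be examined separately.

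The cost is wording in a few sections, possibly one field on a form, and continued data collection on a handful of knees. The change concerns data collection and analysis only, not treatment.
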